12.4.2. Suspected Unexpected Serious Adverse Reaction (SUSAR)

A SUSAR is a serious adverse reaction, the nature and severity of which is not consistent with the reference safety information set out in the Investigator's Brochure.

The Sponsor will be responsible for reporting all SUSARs to the relevant authorities, and other parties, as applicable.

Investigators will be informed of all SUSARs for the relevant IMP for all studies sponsored by Blue Earth Diagnostics, Ltd, whether or not the event occurred in the current study.

12.4.3. Pregnancy

In the unlikely event of a pregnancy arising from sexual conduct performed within 24 hours following IMP administration, it will require expedited reporting to the sponsor's pharmacovigilance department within the same timelines as an SAE. Women who become pregnant between the Screening visit and Visit 2 should be withdrawn from the study. All reported pregnancies in study participants should be followed and the outcome reported using the same form. If the outcome of the pregnancy meets any of the criteria for seriousness, it must also be reported as an SAE. Examples of pregnancy outcomes that are SAEs:

- Reports of congenital anomalies or developmental delay, in the fetus or the child.
- Reports of fetal death and spontaneous abortion.
- Reports of suspected adverse reactions in the neonate that are classified as serious.

13. DISCONTINUATION AND REPLACEMENT OF SUBJECTS

13.1. Discontinuation/Withdrawal from the Study

Subjects are free to withdraw from participation in the study at any time, for any reason, specified or unspecified, and without prejudice.

An investigator may discontinue or withdraw a subject for the following reasons:

- Significant protocol violation or non-compliance.
- If any clinical AE, laboratory abnormality, or other medical condition or situation occurs such that continued participation in the study would not be in the best interests of the subject (investigator decision).
- Protocol violation requiring discontinuation of study treatment.
- If the subject meets the exclusion criteria (either newly developed or not previously recognized) that precludes further study participation.
- Lost to follow-up.
- Sponsor request for early termination of study.
- Subject requests to be withdrawn from the study.
- Positive pregnancy test (females).

The reason for subject discontinuation or withdrawal from the study, if known, will be recorded in the subject's source documents and in the eCRF.

Refer to [Section 10.7](#) for early withdrawal procedures.

13.2. Replacement of Subjects

Subjects who sign the informed consent form (ICF) and do not receive the study scan may be replaced. Subjects who sign the ICF and receive the study scan, but the scan is not considered evaluable (refer to [Section 11](#) of the Imaging Protocol), may be replaced. Subjects who sign the ICF, and receive the study scan, and subsequently withdraw early (as defined in [Section 10.7](#)), or are withdrawn or discontinued from the study, may be replaced.

13.3. Lost to Follow-up

A subject will be considered lost-to-follow-up if there are no follow-up data at Visit 5 (183 days \pm 14 days) and the subject is unable to be contacted by the study site staff. Death will not be considered lost to follow-up.

The following actions must be taken if a subject fails to complete a required study visit:

- The site will attempt to contact the subject and reschedule the missed visit (if within acceptable visit windows), and ascertain if the subject wishes to and/or should continue in the study.
- Where a pre-scheduled Visit 4/Day 3-22 SoC biopsy/neurosurgical intervention is planned, the site will attempt to contact the subject and reschedule the missed visit prior to the SoC biopsy/neurosurgical intervention, and ascertain if the subject wishes to and/or should continue in the study.

- Before a subject is deemed lost to follow-up, the investigator or designee will make every effort to regain contact with the subject (where possible, 3 telephone calls and, if necessary, a certified letter to the subject's last known mailing address or local equivalent methods). These contact attempts should be documented in the subject's medical record or study file.
- Should the subject continue to be unreachable, he or she will be considered to have withdrawn from the study with a primary reason of lost to follow-up. A subject will be considered unreachable when:
 - Has received IMP and is beyond 183 days post-IMP administration.
 - Has not received IMP and is beyond 42 days of pre-study SoC MRI.

14. PROTOCOL VIOLATIONS

A protocol violation occurs when the subject, investigator, or Sponsor fails to adhere to significant protocol requirements affecting the inclusion, exclusion, subject safety and primary endpoint criteria. Protocol violations for this study include, but are not limited to, the following:

- Failure to meet inclusion/exclusion criteria.
- Use of a prohibited concomitant medication.
- Use of a non-validated PET scanner or imaging technique.

Significant non-compliance from Good Clinical Practice (GCP) guidelines will also result in a protocol violation. The Sponsor will determine if a protocol violation will result in withdrawal of a subject.

When a protocol violation occurs, it will be discussed with the investigator and reported to the Sponsor for further assessment of the violation and any potential impact on ongoing protocol requirements and/or on the utility of the subject's collected study data.

15. STATISTICAL METHODS AND CONSIDERATIONS

Prior to database lock and analysis of the final study data, a detailed Statistical Analysis Plan (SAP) will be prepared and approved, describing all the analyses to be performed. The SAP will document any changes to the analyses described below. Continuous data will be summarized using mean, standard deviation, median, and minimum and maximum values. Categorical data will be summarized using frequency counts and percentages.

15.1. Estimation of Sample Size

Approximately 150 subjects will be enrolled, to obtain 130 evaluable subjects.

A one-sample binomial exact test will be used to test the following hypotheses in NPA and PPA of ¹⁸F-fluciclovine PET:

NPA

- $H_0(\text{NPA})$: NPA of PET $\leq \text{NPA}_0$
- $H_1(\text{NPA})$: NPA of PET $> \text{NPA}_0$

PPA

- $H_0(\text{PPA})$: PPA of PET $\leq \text{PPA}_0$
- $H_1(\text{PPA})$: PPA of PET $> \text{PPA}_0$

Where NPA_0 and PPA_0 are performance goals for NPA and PPA, respectively.

Performance goals of 50% (NPA_0) for NPA and 50% (PPA_0) for PPA were selected as acceptable thresholds given the setting where SoC imaging is already equivocal. The lower limits for the exact 95% confidence intervals (CI) (Clopper-Pearson method) for both NPA and PPA should be greater than 50%. Assuming an NPA of at least 70% and a PPA of at least 70% for ¹⁸F-fluciclovine PET would need to be observed, a sample size of 130 would achieve 90% power at a 1-sided significance level of 0.025 to reject the performance goals for both NPA and PPA; assuming a brain metastasis prevalence rate of 0.5.

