	
will be presented for the initial read vs re-read of a subset of PET scans for each reader.
 
Analysis of Safety
 
Safety will be assessed from the time of ¹⁸F-fluciclovine administration until 1 day post-¹⁸F-fluciclovine administration based on reported serious and non-serious adverse events (SAEs and AEs, respectively).
 
For the evaluation of safety, TEAEs are defined as those AEs with onset after the dose of IMP, or existing events that worsened after the dose of IMP during the study, up to 1 day following IMP administration. Verbatim terms of the AEs will be coded to preferred terms (PTs) and system organ classes (SOCs) using the latest version of Medical Dictionary for Regulatory Activities (MedDRA), for data summary purposes. Severity of AEs will be graded using the NCI-CTCAE v5.0. The frequency of TEAEs will be summarized overall, by SOC and PT, and by severity. IMP-related AEs and SAEs will also be summarized.

Rationale for Number of Subjects
	
A one-sample binomial exact test will be used to test the following hypotheses in NPA and PPA of ¹⁸F-fluciclovine PET:
 
NPA
 
 • $H_0(NPA)$: NPA of PET $\leq NPA_0$ • $H_1(NPA)$: NPA of PET $> NPA_0$ 
PPA
 
 • $H_0(PPA)$: PPA of PET $\leq PPA_0$ • $H_1(PPA)$: PPA of PET $> PPA_0$ 
Where NPA_0 and PPA_0 are performance goals for NPA and PPA, respectively.
 
Performance goals of 50% (NPA_0) for NPA and 50% (PPA_0) for PPA were selected as acceptable thresholds given the setting where SoC imaging is already equivocal. The lower limits for the exact 95% CIs (Clopper-Pearson method) for both NPA and PPA should be greater than 50%. Assuming an NPA of at least 70% and a PPA of at least 70% for ¹⁸F-fluciclovine PET would need to be observed, a sample size of 130 would achieve 90% power at a 1-sided significance level of 0.025 to reject the performance goals for both NPA and PPA, assuming a brain metastasis prevalence rate of 0.5.

STUDY SCHEMA

Figure 1. Schema of Study Design

*As applicable; Visit 4 may not apply to all subjects.

IMP, investigational medicinal product; MRI, magnetic resonance imaging; PET, positron emission tomography; SoC, standard of care.

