Limited clinical research has been conducted with other amino acid PET tracers in brain metastases, possibly in part due to their highly limited availability in the US. Studies of brain metastases with amino acid PET tracers ¹⁸F-fluoro-ethyltyrosine (¹⁸F-FET), ¹⁸F-fluoro-dihydroxyphenylalanine (¹⁸F-FDOPA) and ¹¹C-methionine have all been described, with demonstration of increased tracer uptake and sensitivities of 79% to 95%, specificities of 84% to 93% for the detection of brain metastases where MRI is suggestive of recurrent disease (Terakawa, 2008; Galldiks, 2012; Lizarraga, 2014; Ciccone, 2015; Minamimoto, 2015; Romagna, 2016; Ceccon, 2017). In recent recommendations by the RANO working group, amino acid PET was recommended as useful in distinguishing post-therapeutic reactive changes following radiotherapy from recurrent brain metastases (Galldiks, 2019). This was based on review of Level 2 evidence on ¹⁸F-FET, ¹⁸F-FDOPA and ¹¹C-methionine. Transport mechanisms of these tracers have overlap with ¹⁸F-fluciclovine, in that these are predominantly LAT1-mediated. Furthermore, known cross-affinity for various amino acids between the 2 transporters support the expectation for ¹⁸F-fluciclovine to demonstrate comparable performance in brain metastases, akin to other amino acid PET tracers and known ¹⁸F-fluciclovine imaging characteristics in glioma. Thus, the investigation of ¹⁸F-fluciclovine in the imaging of brain metastases is of considerable clinical relevance, particularly when considering promising results from the aforementioned IITs of ¹⁸F-fluciclovine in brain metastases.

Amongst the previously cited studies using ¹⁸F-FET, ¹⁸F-FDOPA and ¹¹C-methionine, different interpretation criteria for optimum detection of disease recurrence have been reported. Furthermore, these criteria have been based on different methods of quantifying

PET tracer uptake, and in the case of ¹⁸F-FET, incorporate the interpretation of dynamic scan data (time-activity curves). Therefore, existing heterogeneous data on optimum image interpretation criteria in other amino acid PET tracers cannot be directly applied to ¹⁸F-fluciclovine. Within this clinical program, BED is conducting a Phase 2 study (BED-FLC-219) designed to define image interpretation criteria.

¹⁸F-fluciclovine has a well-established safety profile and a wide distribution network in the US where it is routinely used as standard of care (SoC) for imaging in biochemical recurrence of prostate cancer.

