15.5. Analysis of Primary Endpoint

The primary endpoint for the study is subject-level NPA and PPA (equivalent to specificity and sensitivity, respectively) of ¹⁸F-fluciclovine PET in detecting recurrent brain metastases. Subject-level NPA and PPA will be calculated based on BIE of ¹⁸F-fluciclovine PET compared to SoR on the reference lesion.

Where NPA_0 and PPA_0 are performance goals for NPA and PPA, respectively. Performance goals of 50% (NPA_0) for NPA and 50% (PPA_0) for PPA were selected as acceptable thresholds given the setting where SoC imaging is already equivocal. The analyses for NPA and PPA will be performed using the one-sample binomial exact test. In addition to the rates, exact two-sided 95% CIs according to the Clopper-Pearson method will also be provided. If the pre-defined NPA and PPA goals are met by the same two of three readers (both tests reach statistical significance for the same two readers), the study will be considered to have successfully demonstrated the effectiveness of ¹⁸F-fluciclovine PET in detecting recurrent brain metastases.

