7.4 Efficacy Evaluation

7.4.1 *Datasets Analyzed*

All efficacy summaries will be based on the FAS. A data listing of subjects excluded from the FAS, to include the reason for exclusion, will be presented.

7.4.2 *Measurements of Treatment Compliance*

Not applicable. This is a single dose study, administered by site staff.

7.4.3 *Primary Efficacy Endpoint Analysis Methods*

The primary endpoint for the study is subject-level NPA and PPA (equivalent to specificity and sensitivity, respectively) of ¹⁸F-fluciclovine PET in detecting recurrent brain metastases.

Subject-level NPA and PPA will be calculated based on BIE of ¹⁸F-fluciclovine PET compared to SoR on the reference lesion. Imputations for SoR indeterminate findings will be performed according to section 7.4.5.1.

The analyses for NPA and PPA will be performed using the one-sample binomial exact test to test the following hypotheses:

NPA

- $H_0(NPA)$: NPA of PET $\leq NPA_0$
- $H_1(NPA)$: NPA of PET $> NPA_0$

PPA

- $H_0(PPA)$: PPA of PET $\leq PPA_0$
- $H_1(PPA)$: PPA of PET $> PPA_0$

where NPA_0 and PPA_0 are performance goals for NPA and PPA, respectively. Performance goals of 50% (NPA_0) for NPA and 50% (PPA_0) for PPA have been selected as acceptable thresholds given the setting where SoC imaging is already equivocal.

Exact two-sided 95% CIs according to the Clopper-Pearson method will be provided. If the pre-defined NPA and PPA goals are met by the same two of three readers (both tests have lower limits for the exact 95% confidence intervals greater than 50% for the same two readers), the study will be considered to have successfully demonstrated the effectiveness of ^{18}F -fluciclovine PET in detecting recurrent brain metastases.

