7.4.5 Statistical/Analytical Issues

7.4.5.1 Handling of Dropouts or Missing Data

Data imputation on missing or indeterminate SoR from the Central Truth Panel on the reference lesion (i.e. subject level only) will be performed according to the following chart:

If the SoR determined by the CTP is not positive/negative then the SoR will be determined using the following rules:

1. If the subject has neurological deterioration at any time during the 6-months follow-up, the SoR will be assigned to positive.
2. If the subject is confirmed not to have neurological deterioration on or after day 141 (6 months with a 4-week time window, i.e. day 169 with a 28-day time window), even if the subject dies after day 141, the SoR will be assigned to negative.
3. Otherwise the SoR will remain as indeterminate.

All subject-level analysis involving SoR will be presented twice, by imputing the remaining indeterminate results as follows:

1. Main analysis of primary and secondary endpoints on subject level diagnostic performance – for each PET reader, the worst case according to that reader (i.e. the opposite finding to the individual PET reader finding) will be imputed
2. Sensitivity analysis 1 of primary and secondary endpoints on subject level diagnostic performance - for each PET reader, the worst case according to the majority of PET readers (i.e. the opposite finding to the PET finding of at least 2/3 PET readers)

To check the validity of the results based on the site's determination of the reference equivocal lesions, these lesions will be measured and confirmed by the central neuroradiologist. A sensitivity analysis on the main endpoint of subject level PPA and NPA, using only subjects with central neuroradiologist confirmation of the reference equivocal lesions, will be performed if there is discrepancy between the site confirmation of reference equivocal lesions vs the central neuroradiologist confirmation.

For lesion level analysis, none of the lesions will be imputed if the SoR designation from the CTP is missing or indeterminate. Lesion-level analysis will only include lesions with SoR designation of positive or negative by the CTP.

7.4.5.2 *Interim Analyses and Data Monitoring*

Not applicable.

7.4.5.3 *Multicenter Studies*

This is a multicenter study, with approximately 18 sites expected to participate. Data collected from all study sites will be pooled for data analysis.

7.4.5.4 *Multiple Comparisons/Multiplicity*

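### The stated 90% power for both NPA and PPA is about the power for one goal; for one reader, 130 subjects give at most 83% for both

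*Protocol*

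**What the plan says.** Protocol 15.1 plans about 150 enrolled subjects to obtain 130 evaluable. It specifies a one-sample exact binomial test for each of NPA and PPA, performance goals of 50%, assumed rates of 70%, one-sided alpha 0.025 and prevalence 0.5. On these inputs it says that 130 subjects "would achieve 90% power at a 1-sided significance level of 0.025 to reject the performance goals for both NPA and PPA". The synopsis makes the same claim ("reject the performance goals for both NPA and PPA, assuming a brain metastasis prevalence rate of 0.5"), and SAP 7.6 repeats it.

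The success rule is in Protocol 15.5 and SAP 7.4.3. Both goals must be met by two of the three readers, and by the same two: "both tests reach statistical significance for the same two readers" in the protocol, "If the pre-defined NPA and PPA goals are met by the same two of three readers" in the SAP. The sample-size text mentions neither the readers nor any correlation between them, and neither document shows how the 90% was derived.

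**The concern.** The power sentence names both goals, and success requires both. A reader will therefore take 90% as the chance of meeting both when true NPA and PPA are 70%. If 90% is instead the chance of meeting one of them, the chance of meeting both is lower. This sentence is the only quantitative justification for the sample size, and it appears in three places.

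The same sentence has a smaller fault. It says that 70% on "PET would need to be observed, a sample size of 130" and so on, as if 70% were a result the trial must show. It is the assumed true rate; the observed rate needed to pass is lower.

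**Working it through.** **Inputs**, all from Protocol 15.1 (SAP 7.6 is the same): N = 130; exact binomial test; null rate 0.5; true rate 0.7; one-sided alpha 0.025; prevalence 0.5, so 65 subjects positive and 65 negative by the standard of reference.

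**Step 1: cutoff for one goal, n = 65.** P(X ≥ 41 | 0.5) = 0.0232 and P(X ≥ 40 | 0.5) = 0.0408, so the test rejects at 41 or more. The confidence-interval criterion agrees: the Clopper-Pearson lower limit is 0.502 at 41/65 and 0.486 at 40/65. The smallest passing observed rate is 41/65 = 63.1%.

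**Step 2: power for one goal.** P(X ≥ 41 | 0.7) = 0.910. This is the quantity that comes close to the stated 90%. Averaged over a random split, with the number of positives m ~ Binomial(130, 0.5), it is 0.890.

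**Step 3: power for both goals, one reader.** PPA uses only reference-positive subjects and NPA only reference-negative subjects (SAP 6.4.1.1). Given the split, the two tests are independent and joint power is the product:

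- At 65/65: q = 0.910 × 0.910 = 0.828.
- Over every split m/(130 − m), the maximum of power(m) × power(130 − m) is 0.828, at 65/65. No split reaches 0.90.
- Averaged over the random split: 0.792.
- Over the central 95% of splits (54 to 76 positives), q runs from 0.758 (55/75) to 0.828.

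**Step 4: could another calculation give 90% jointly?** At 65/65 and one-sided 0.025, the normal approximations give 0.798 (continuity-corrected), 0.833 (arcsine), 0.839 (score) and 0.884 (Wald). The exact test at one-sided 0.05 gives 0.893, but that is not the stated alpha.

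**Step 5: the two-of-three-reader rule.** Assume that all three readers have true rates of 70%. If they are independent, the probability that at least two meet both goals is 3q² − 2q³. If they are identical, it is q.

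| Split | One reader, both goals (q) | Two of three, independent |
|---|---|---|
| 65/65 | 0.828 | 0.922 |
| 63/67 | 0.826 | 0.920 |
| 58/72 | 0.820 | 0.914 |
| 56/74 | 0.810 | 0.905 |
| Random-split average | 0.792 | 0.887 |

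At every other split the independent-reader figure is below 0.90. The four splits listed, with their mirrors, have total probability 0.308. For intermediate dependence, a simulation with an assumed latent-Gaussian model of reader correctness gives, at 65/65 and averaged over a random split respectively: 0.909 and 0.876 at kappa 0.26; 0.900 and 0.864 at 0.37; 0.881 and 0.845 at 0.49; 0.868 and 0.829 at 0.64.

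**Step 6: what would give 0.90 for both goals, one reader?**

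- By sample size, averaged over a random split: 0.899 at N = 163 and 0.901 at N = 164.
- By sample size, even split: 0.903 at N = 158, then 0.894 at 159, 0.886 at 160 and 0.901 at 161. It stays at or above 0.90 from 161 up to 280, the largest N checked.
- If all 150 enrolled subjects were evaluable: 0.869 (75/75) or 0.865 (random-split average).
- By true rate at N = 130: 71.6% for both (65/65) or 72.3% (random-split average).

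**The case against.** **Both may mean each.** The sentence follows two separately stated hypothesis pairs. Read as power for each goal, 90% is right (0.910). But success needs both goals, so joint power is the natural reading. If each was meant, the sentence is still not the power of the success criterion and still needs rewording.

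**The headline is a one-reader figure.** It equals the trial's chance of success only if the readers are identical. At 65/65 the two-of-three rule gives 0.83 to 0.92, which contains 0.90, and the simulated values at kappa 0.26 and 0.37 are 0.909 and 0.900. This stands: 90% is not out of reach at study level. It does not rescue the text, because the power statement mentions no readers and the plan assumes no correlation. Averaged over a random split, even independent readers give only 0.887. The ends of the range are not strict bounds either; they assume equal reader accuracy and no negative dependence.

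**Random-split averaging is a choice.** Computing at the expected 65/65 is ordinary practice, and leaving out the averaging is no error. But 65/65 is already the most favourable split for one reader, and it gives 0.828.

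**The consequence is modest.** This also stands. An overstated power biases no estimate and permits no false claim of success, and the plan assumes rates of at least 70%. At the low end of what Protocol section 2 cites for related tracers (79% sensitivity, 84% specificity), joint power for one reader is above 0.99.

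**Conclusion.** The power statement is wrong as written. At the planning assumptions, 130 evaluable subjects give 0.91 power for each goal. For one reader, they give 0.83 for both at 65/65 and 0.79 averaged over a random split. The chance that a given reader misses at least one goal is therefore 17% to 21%, not 10%. That the 90% began as a one-goal figure is an inference from the match, since no derivation is shown.

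The one-reader figures rest only on the plan's stated inputs. The study-level range (0.83 to 0.92 at 65/65; 0.79 to 0.89 averaged over a random split) also assumes that every reader has true rates of 70% and that dependence lies between independent and identical. All figures leave out the SAP 7.4.5.1 rule for subjects whose reference standard stays indeterminate, under which "the worst case according to that reader (i.e. the opposite finding to the individual PET reader finding) will be imputed". That would lower power, by an amount that cannot be computed because the documents give no indeterminate rate.

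This should be corrected, but it does not threaten the validity of the primary analysis.

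**What to change.** In the synopsis, Protocol 15.1 and SAP 7.6, replace the power sentence with text along these lines:

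> Assuming true NPA and PPA of 70% and prevalence 0.5, 130 evaluable subjects give 91% power for each goal at a 65/65 split (89% averaged over a random split). For a given reader, power to meet both goals is 83% at a 65/65 split (79% averaged over a random split).

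Add the power under the two-of-three-reader rule as a range from identical to independent readers (0.83 to 0.92 at 65/65; 0.79 to 0.89 averaged over a random split), and state the assumptions on reader correlation and equal reader accuracy. Describe 70% as the assumed true rate, not as a rate that must be observed.

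This is wording only. The test, type I error, success rule and enrolment stay as they are; the cost is a less favourable stated power.

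If the sponsor does intend 90% for both goals per reader, the alternative is about 164 evaluable subjects. At the plan's own yield that is 164 × 150/130 ≈ 189, so about 190 enrolled, or about 40 more than planned. That target is stricter than the success rule unless the readers are identical, so rewording is the proportionate change.
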